1.7 Autonomic nervous system (ANS) evaluation

Cardiovagal evaluation: Continuous electrocardiogram recording using surface electrodes will monitor changes in heart rate during deep breathing at 6 cycles per minute, Valsalva manoeuvre and bipedestation.

Sympathetic adrenergic evaluation: Continuous blood pressure (CNS systems) and manual pressure recording will monitor changes during Valsalva manoeuvre, isometric activity and standing up (or passive inclination if the subject is unable to remain standing up without support).

Sympathetic cholinergic evaluation: Using surface electrodes applied to the hand and foot of the subject we will record the change of skin conductance to low-intensity electrical stimuli on the median or posterior tibial nerve, deep inspiration and startle (sympathetic skin response). A specific questionnaire for the assessment of dysautonomic symptoms (Composite Autonomic Symptoms Scale COMPASS 31) will be administered.

1.8 Electromyography (EMG).

A little needle recording electrode will be inserted into different muscles from cranial (*orbicularis oris*), cervical (*extensor indicis proprius*) and lumbar (*tibialis anterior*) segments. Electrical signal from individual muscle fibers and motor units both at rest and during voluntary contraction will be recorded.

1.9 Brainstem reflex

Trigeminal blink reflex, mediated by trigemino-facial ponto-medullary-circuits will be assessed. Surface recording electrodes will be attached over the *orbicularis oculi* in both sides with active electrode over the middle part of the lower eyelid and the reference at the lateral canthus of the eye. Stimulating electrodes will be placed over the supraorbital nerve. Ipsilateral (R1, R2) and contralateral responses (R2c) latencies measured in ms will be analyzed.

2) Development an animal model of anti-LGI1 encephalitis using active immunization

2.1. Behavioral studies. From baseline (pre-immunization) until day 71 (euthanized) animals will be regularly tested with an extensive panel of memory/behavioral paradigms, as reported in our model of passive transfer of antibodies (*Petit-Pedrol et al., Brain 2018;141:3144-59*).

2.2. Effects on LGI1. The antibody effects will be determined in subsets of mice euthanized at day 42 (acute phase) and the rest of mice on day 71 (chronic phase). Sections of cortex/hippocampus will be examined using (1) confocal microscopy and IMARIS software to quantify the total surface and synaptic clusters of LGI1 and their synaptic protein partners (Kv1.1 and AMPA receptor), and (2) electrophysiology to assess hippocampal long-term (LTP) and short-term potentiation (STP). These techniques were described in detail in our passive immunization models of NMDAR and LGI1 antibodies (*Planagumà et al., Brain* 2015;138:94-109; *Petit-Pedrol et al., Brain* 2018;141:3144-59).

2.3. Immune cells and immune-inflammatory pathways. From tissue samples obtained on days 42 and 71, immune/ inflammatory cells (B, T, activated microglia, etc.) will be examined by immunohistochemistry with antibodies specific for the indicated cell types, as reported (Planagumà et al., *Brain* 2015;138:94-109). RNA will be extracted from brain for RNA/NanoString analysis targeting the same genes as described in patients (see Annex Table), with mice-RNA primers. Findings from the acute stage (day 42) will be compared with the post-acute stage (day 71).

5 Design of the study

Human studies

Clinically characterization of the post-acute stage of anti-LGI1 encephalitis: Prospective single center, single arm, national study of 3 years duration.

Our already established multidisciplinary team has extensive experience in developing similar studies on patients with autoimmune encephalitis, and the results have been so far satisfactory from both a scientific perspective and for patients. In specific, the study will be conducted following the protocol that we developed for previous prospective longitudinal observational studies performed between 2017 and 2022 with patients with anti-NMDAR encephalitis during the post-acute stage (**Study title: "Immune-mediated diseases of the synapse: symptoms, brain networks, and the link to human memory"; PI: [name]; Code: HCB/2016/0596**), and with patients with anti-LGI1 encephalitis during the post-acute stage (**Study title: "A Translational Model of Antibody-mediated Synaptic Disease: Symptoms, Neuronal Circuits, and the Mechanisms of Memory Loss and Recovery"; PI: [name]; Code: HCB/2018/0561**), that will serve as the control group. No new visits will be necessary in this control group.

The cognitive rehabilitation program will be implemented following the same protocol and tools that we are currently using in a very similar study but with patients with anti-NMDAR encephalitis (**Study title: "Antibody-mediated NMDA receptor encephalitis: symptoms, biomarkers, and mechanisms of the prolonged recovery stage"; PI: [name]; Code: HCB/2022/1070**). All of them had been accordingly approved by the CEIm of HCB.

Development an animal model of anti-LGI1 encephalitis using active immunization

Experimental design. Mice C57BL/6J, 8-10 weeks old will be used. All mice will be immunized twice (days 0 and 28) with a mixed combination of selected LGI1 peptides (see Annex text, and Annex Fig E). As adjuvant, we will use Addavax+Pertussis toxin that primes B-cell and antibody responses with better tolerability than Freund's adjuvant. In an experimental model of anti-NMDAR encephalitis, this approach resulted in very high titers of NMDAR antibodies with

reactivity similar to that of patients' antibodies (see first section, "Previous Activitatis"). The corresponding control group will receive only Addavax+Pertussis toxin without peptide. The total number of mice including those for the selection of peptides, controls, sets of animals sacrificed on days 42 and 71, and subsets needed for acute brain slices for electrophysiology and fresh tissue for NanoString/RNA studies is 104.

6. Selection of participants

1.1. Patient recruitment and number of patients. 20 LGI1 patients will be recruited: families and patients will be approached during the acute phase of the disease and invited to participate in the study after hospital discharge.

Identification of patients will be done in (1) our hospital, (2) through a network of Spanish hospitals (already in place), and (3) the Neuroimmunology lab at HCB/IDIBAPS (referral center for autoimmune encephalitis). Informed consent and general information through a structured questionnaire will be obtained from participants/legal guardians. Regarding the number of patients, we have selected 20 patients based on our published experience with another autoimmune disease (NMDAR encephalitis) and a previous pilot study with anti-LGI1 encephalitis (used as external control group who did not have remote cognitive training). In both studies, the number of ~20 patients was informative.

Exclusion criteria include: patients unable to travel to our center, and previous history of psychiatric or neurologic diseases (eg, schizophrenia, dementia, stroke) that may interfere with the proposed studies. All patients will have a preliminary assessment of their interest in participation and any of the indicated incompatibilities

7. Treatment and calendar of the study

In-person visits include 3 visits during the post-acute stage:
V1 (after hospital discharge, ~1-3 weeks after symptom onset),
V2 (6 months),
and V3 (1 year) (Fig D).

[figure not shown]
Each visit consists of ~1 day and 1 night at Hospital Clínic (distributed in 1/2 day, 1 night, and 1/2 day) during which they undergo clinical assessments and tests according to a pilot study: neurologic and cognitive assessment, EEG, ANS, EMG, brainstem reflex study and video-polysomnography. At V2 we will obtain an MRI (to compare with that of the acute phase). We will also obtain and the blood and serum. During the post-acute stage (by the time that patients will come to Hospital Clínic de Barcelona), blood and CSF samples will be obtained for identical studies as those performed in the acute stage serum and CSF samples. Two lumbar punctures (LP) will be performed, after informed consent, one at the first presential visit (V1) and the other at the last presential visit (V3). After the first visit, patients/families will be instructed to keep remote cognitive training for 6 months. The frequency of cognitive training is suggested by data from our pilot study in which 90% of patients had cognitive abnormalities at V1 and the improvement (albeit partially; without cognitive training) mainly occurred during the first 6 months. These patients will serve as external controls.

Summary:

V1: neurologic and cognitive assessment, EEG, ANS, EMG, brainstem reflex study and video-polysomnography. Blood and serum examination. Lumbar puncture

V2: neurologic and cognitive assessment, EEG, ANS, EMG, brainstem reflex study and video-polysomnography. MRI. Blood and serum examination

V3: neurologic and cognitive assessment, EEG, ANS, EMG, brainstem reflex study and video-polysomnography. Blood and serum examination. Lumbar puncture

Presential visits

- Presential standard neuropsychiatric examinations and cognitive assessments will be conducted as per routine clinical practice and with a reported panel of neurological functional, cognitive and psychiatric tests. Total time ~4h spread over 3 visits (the exact timetable can be adapted to patients' preferences and the length of the interviews will vary according to patients' clinical status; the times are indicative and are overestimated to be sure). These clinical evaluations will take place in the same room where the patients will sleep, and patients will have enough pauses in between to rest, eat/drink and go for a walk outside the hospital with their relatives.
- Psychophysical testing of working memory: The duration of this task depends on the performance of the patients; maximum ~1:30h. It will be done in the same room during V1 (1st visit in our center), V2 (6 months follow-up) and V3 (1 year follow-up).
- MRI studies. It is a passive examination, patients will not need substantial mental or physical efforts. Total time ~45min during V2 (6 months follow-up).
- PSG: It is a passive examination, patients will not need substantial mental or physical efforts. Patients will sleep in the same room where the other clinical examinations and psychophysical testing will be carried out, so they will get used to and adjust to the environment during the day. Total time: night sleep during V1 (1st visit in our center), V2 (6 months follow-up) and V3 (1 year follow-up).
- ANS: It is an active examination. Patients will perform simple and non invasive exercises regarding deep breathing, blowing and standing up.
- EMG: It is a passive examination, patients will not need substantial mental or physical efforts.
- Brainstem reflex: It is a passive examination, patients will not need substantial mental or physical efforts.
- EEG: It is a passive examination, patients will not need substantial mental or physical efforts. Total time ~45min during V1 (1st visit in our center), V2 (6 months follow-up) and V3 (1 year follow-up).
- Actimetry: It is a passive examination, patients will not need substantial mental or

physical efforts. Total time: one week after V1 (1st visit in our center), V2 (6 months follow-up) and V3 (1 year follow-up).

- Lumbar Puncture will be performed, after informed consented, one at the first presential visit (V1) and the other at the last presential visit (V3).
- Brain recordings - It is a passive examination, patients will not need substantial mental or physical efforts. Total time: night sleep.
- Patients' blood and serum will be examined at the time of diagnosis (sent from local hospitals to our center via courier) and at the post-acute stage: V1 (1st visit in our center), V2 (6 months follow-up) and V3 (1 year follow-up). It will be performed in the same room; total time ~30min

Remote cognitive rehabilitation program will be performed through an online validated platform (Guttmann Neuropersonal Trainer [GNPT]: <https://gnpt.es/>) run by our team. This is a Sanitary Product with CE certification (Producto Sanitario RPS/430/2014; International Patent [PCT/ES2008/00677]) and here will be used within its approved indications. The rehabilitation program will increase in difficulty and decrease in frequency during the six months of follow-up (V1-V3).

Patients/families will be instructed to perform remote cognitive rehabilitation during the presential visits. Patients will be able to use their personal computer and access via an available link and a user code the GNPT platform. In case that they do not have easy access to adequate equipment to access the platform, we will provide the iPad tablet with all the necessary software installed and ready to use to support their training. The indicated frequency of cognitive training is based on results of a recently published pilot study in which patients were followed with only presential visits (no remote visits or cognitive training was provided). The study showed that a slow progressive cognitive improvement occurred in most patients during the 1 year follow-up. However, the improvement was more marked during the first 6 months compared with the last 6 months. This finding suggested that intensive cognitive training (particularly during the first 6 months) could accelerate recovery and improve outcome. Accordingly, for the current study patients will undergo cognitive rehabilitation twice per week for the first 3 months and once per week for the last 3 months. Similar programs are currently used by our team for patients with multiple sclerosis (along with collaborations with Institute Guttmann, Barcelona). Remote cognitive sessions will take ~45-60min.

8. Statistics

Human studies: Cross-sectional comparisons among the 2 groups of patients will be done with Analysis of Covariance (ANCOVA) and Chi-Squared tests, as appropriate. Post-hoc analyses with Bonferroni correction for post-hoc multiple comparisons will be applied to all analyses. Analysis of inter- and intragroup differences in the longitudinal follow-up will be done using multilevel linear mixed-effect (LME). Lme4 R package (version 1.1-27.1) will be used to fit LME models. Comparisons will be done with emmeans library (version 1.7.3) and Tukey method for post-hoc correction for multiple testing. The global tendency of recovery of cognitive deficits in patients receiving or not cognitive training will be assessed with the Cochran-Armitage test for trend. All analyses will be addressed considering a two-tailed type I error of 5% with statistical

significance set at p-value <0.05, using SPSS (version 25; IBM Corp, Armonk, NY) and R package (version 4.1.2; Vienna), as previously reported (*Guasp et al., Lancet Neurol 2022;21:899-910*).

Animal studies: Animal behavior with multiple determinations in time (e.g., recognition of new object) will be analyzed using repeated measures two-way analysis of variance (ANOVA). Behavioral studies with a single time determination (e.g., depressive behavior) will be analyzed with one-way ANOVA or Mann-Whitney-U for skewed distributions (e.g., tail suspension). The intensity of IgG deposits in brain and electrophysiological studies (long-term potentiation) will be analyzed with two-way ANOVA. The reactivity intensity of the antibodies of patients in HEK cells (CBA), neuron cultures, or brain tissue, or quantification of synaptic markers (e.g., GluN1, PSD95) or activated microglia, in a single time determination, will be analyzed by one-way ANOVA. Post-hoc analyses for all experiments will use Bonferroni correction for multiple testing. A p value of <0.05 will be considered significant and the α -error will be set to 0.05. Analyses will be done with GraphPad Prism v7 (*Planagumà et al., Ann Neurol 2016;80:388*).

9. Risks and benefits for participants in the study

It is possible that patients will not benefit from participating in this study. However, based on the results of previous similar studies (“Immune-mediated diseases of the synapse: symptoms, brain networks, and the link to human memory”, IP: [name], Code: HCB/2016/0596; “A Translational Model of Antibody-mediated Synaptic Disease: Symptoms, Neuronal Circuits, and the Mechanisms of Memory Loss and Recovery”, IP: [name], Code: HCB/2018/0561) we expect that patients will directly and immediately benefit from their participation in the carefully monitored cognitive training program and the close clinical follow up in an experienced unit.

Our previous studies with this same load of tests in presential visits were successful and patients with anti-NMDAR and anti-LGI encephalitides returned for the most part in successive retest sessions after 3, 6, 12 and even 24 months (Guasp et al. Lancet Neurology 2022; Ariño et al. Neurology 2020; Stein et al. Nat Commun 2020). This demonstrates that the load of tasks and frequency of visits was not unbearable and patients were happy to maintain participation in the project for an extended period of time and repeat sessions with identical task loads. We specifically gauged participant satisfaction in a gathering of participating families at Hospital Clínic in 2018, where we presented the objectives and initial results of the study and allowed participants to ask questions and express their concerns. Participants were very satisfied with the study and appreciated the opportunity to be monitored in the reference center for this disease in Europe, and to get in touch with other families afflicted by the same rare disease. We plan to repeat this experience in the framework of the present project in order to detect possible dissatisfactions with our experimental protocols and adapt them for the comfort of the participants.

Nonetheless, the detailed risks for each of the procedures in the current study are as follows:

- a) **Risks of presential Neurologic, Psychiatric and Cognitive assessments:** These evaluations are innocuous and do not represent any substantial risk for participants. The main risk of these evaluations is fatigue, and they may be demanding in terms of execution time, but patients will be able to take breaks during the testing to alleviate it. Moreover, they will be guided by a member of our team to ensure that it does not cause any major discomfort to the patient.

- b) Risks of Magnetic Resonance Imaging (MRI): The known risks associated with MRI studies are minimal. The procedure uses radio waves and a magnetic field to take pictures. Some individuals may feel claustrophobic (uncomfortable in small areas) during the MRI scan or may be disturbed by the sounds of the machine (which are loud and repetitive). Patients can be given music to listen to during the scan or can hear the voice of the technician. These have been shown to help patients relax during the scan. If the subject experiences these feelings and is uncomfortable, they can always discontinue the scan
- c) Risks of presential EEG studies: EEG is considered a safe procedure and causes no discomfort. During the recording, subjects can relax. Some people may develop a mild rash where the electrodes were attached that resolves without treatment.
- d) Risks of presential ANS, EMG and brainstem reflex: These neurophysiological tests are considered safe procedures which are performed daily in our centre. Discomfort related to electrical stimulation and needle insertion is minimal.
- e) Risks of presential Sleep studies: The same for EEG studies, as well as possible discomfort before falling asleep and reduced night rest. However, the cabling system is optimized to facilitate the free movement of patients at night, and the room is soundproofed.
- f) Risks of Psychophysical testing and Brain recordings: These evaluations are innocuous and do not represent any substantial risk for participants. The main risk of these evaluations is fatigue, reduced night rest, and they may be demanding in terms of execution time. However, they will only be performed in the course of two weeks separated by 6 months, for each participant. The computerized task will have a game component to make it engaging, as well as the device is specifically designed to be comfortable during sleep for nocturnal recordings. In the first day of the week of recordings, a member of our team will make a video-conference with the participant (including family members if they are minors) to assist with the setup of the device for testing and recording.
- g) Risks of Blood Tests: Risks associated with blood drawing include infection, bleeding, bruising, fainting and discomfort.
- h) Risks of Lumbar Puncture: Although lumbar puncture (spinal tap) is generally recognized as safe, it does carry some risks. These include post-lumbar puncture headache that can last from a few hours to a week or more. Lying flat and drinking fluids helps to relieve this headache. Patient may experience temporary back discomfort or pain, and mild bleeding that may occur near the puncture site. These side effects resolve without treatment. It is possible that patients will not benefit from the lumbar puncture, but for those patients with unfavourable clinical evolution or relapse, NMDAR antibody testing in CSF will help guide therapeutic decisions (antibody titers in CSF, but not in serum, have clinical correlation).

9. Ethics and legal aspects

The study will be carried out in compliance with the Helsinki Declaration (current version, Fortaleza, Brazil, October 2013) and in accordance with the protocol and with the relevant legal requirements, which in this case is Biomedical Research Law 14/2007 of July 3, and Regulation 2017/745 on Medical Products. Informed consent will be obtained for all patients before their inclusion in the study, and their samples stored in the IDIBAPS-Hospital Clínic Neuroimmunology Laboratory until they are used for the objectives of this study.

10. Data management

Clinical data from patients will be coded. Each patient will be assigned a code. In another

separate database, the IP will store the relationship between each code and the patient's medical record number.

Coded information from patients will be stored in online Redcap database from HCB (redcap.clinic.cat).

Computers and wearables will be stored at Cellex 3A, Neuroimmunology laboratory.

11. Treatment of data and archiving of registers. Confidentiality of the data

The treatment, communication and transfer of personal data of all participants will comply with EU Regulation 2016/679 of the European Parliament and of the Council of April 27, 2016 regarding the protection of natural persons in terms of the processing of personal data and the free circulation of data, being mandatory as of May 25, 2018. The legal basis that justifies the processing of your data is the consent given in this act, in accordance with the provisions of the Article 9 of EU Regulation 2016/679.

The data collected for these studies will be collected identified only by a code, so no information will be included that would allow the participants to be identified. Only the study doctor and his collaborators with the right of access to the source data (clinical history), may relate the data collected in the study with the patient's medical history. In the future, the data collected and properly coded may be used also to address other questions relevant for the understanding of anti-LGI1 encephalitis, and we will request specific consent for this potential prospective use of the data.

The identity of the participants will not be available to any other person except for a medical emergency or legal requirement.

The health authorities, the Research Ethics Committee and personnel authorized by the study promoter may have access to the identified personal information, when necessary to verify data and study procedures, but always maintaining confidentiality in accordance with current legislation. .

Only coded data will be transferred to third parties and other countries, which in no case will contain information that can directly identify the participant (such as name and surname, initials, address, social security number, etc.). In the event that this transfer occurs, it would be for the same purpose of the study described and guaranteeing confidentiality.

If a transfer of encrypted data takes place outside the EU, either in entities related to the hospital center where the patient participates, to service providers or researchers who collaborate with us, the data of the participants will be protected by safeguards such as contracts or other mechanisms established by the data protection authorities.

As promoters of the project, we undertake to process the data in accordance with EU Regulation 2016/679 and, therefore, to keep a record of the treatment activities that we carry out and to carry out a risk assessment of the treatments we carry out, to know what measures we will have to apply and how to do it.

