- 3) A mouse model of active immunization with LGI1 peptides will reproduce better the disease than a previous model of passive transfer of antibodies that leads to antibody diffusion highly limited to hippocampal regions, absent inflammatory infiltrates, and changes that last for only 12-15 days. In contrast, an active immunization model will lead to inflammatory infiltrates and LGI1-specific B-cell responses involving the entire brain in association with: synthesis of LGI1 antibodies, synaptic alterations mediated by changes on LGI1 and interacting proteins, and behavioral alterations. We postulate that the alterations in all these paradigms will be long-lasting, reproducing not only the acute phase but also the chronic phase of the disease.

4 Objectives and aims of the study

The indicated hypotheses will be tested in **3 objectives**:

- 1)** Determine the main clinical features (neurological, cognitive, EEG, video-polysomnography) of patients with anti-LGI1 encephalitis during the chronic phase of the disease, and assess serum biomarkers of autoimmunity/inflammation (LGI1 antibodies, RNA/NanoString analysis of targeted gene expression related to activation/function of B cells, T cells, microglia, and other interleukin/chemokine signaling) and neuronal degeneration (NfL levels).
- 2)** Assess whether remote cognitive training during the first 6 months following initial hospital discharge modifies clinical outcome. Findings will be compared with a previously studied external control group of patients with anti-LGI1 encephalitis but who did not receive remote cognitive training.
- 3)** Develop an animal model of active immunization using a repertoire of LGI1 peptides derived from the main immunogenic regions of LGI1. Determine the presence of LGI1 antibodies in serum/CSF and brain inflammatory infiltrates using immunohistochemistry. Examine how these immunological alterations alter the pre- and postsynaptic LGI1-interacting proteins (VGKC, AMPA receptor) and cause neurological symptoms; for this we will use confocal synaptic imaging, electrophysiology, and a standard panel of behavioral tests. In addition, we will assess the same serum biomarkers of autoimmunity/inflammation (RNA/NanoString analysis) as those used in patients, but with primers adapted to mouse.

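### Mouse behaviour measured over time goes to a repeated-measures two-way ANOVA, which makes weaker use of the pre-immunisation score than a baseline-adjusted contrast; the cost is power, not false positives

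*Protocol*

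**What the plan says.** Section 8 (Animal studies) assigns a model by type of measurement. For behaviour tested repeatedly: "Animal behavior with multiple determinations in time (e.g., recognition of new object) will be analyzed using repeated measures two-way analysis of variance (ANOVA"). For behaviour tested once: "Behavioral studies with a single time determination (e.g., depressive behavior) will be analyzed with one-way ANOVA or Mann-Whitney-U for skewed distributions". It adds "A p value of <0.05 will be considered significant" and "Post-hoc analyses for all experiments will use Bonferroni correction for multiple testing".

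The schedule is in section 4.1, item 2.1: "From baseline (pre-immunization) until day 71 (euthanized) animals will be regularly tested with an extensive panel of memory/behavioral paradigms". Item 2.2 has a subset of mice euthanised at day 42 and the rest at day 71.

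The comparison is in section 5: all mice in the model are immunised with peptide plus adjuvant, and "The corresponding control group will receive only Addavax+Pertussis toxin without peptide". The same section gives the only sample-size figure. The total, covering peptide selection, controls, both euthanasia days and "subsets needed for acute brain slices for electrophysiology and fresh tissue for NanoString/RNA studies is 104". There is no split by group and no power calculation.

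The protocol does not say how the pre-immunisation test enters the ANOVA, which ANOVA effect decides, or how many paradigms and time points there are.

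**The concern.** A two-way repeated-measures ANOVA with group and time as factors gives a group effect, a time effect and a group-by-time interaction. If the pre-immunisation test is one of the time levels, neither test that bears on the peptide is well aimed. The group effect averages over a time point where the true difference is zero. The interaction spends its degrees of freedom on every pattern of change over time, when the question is whether mice differ after immunisation given where they started.

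What is at stake is the behavioural part of hypothesis 3. The 104 mice are shared among several experiments, so groups in any one behavioural test may be small. A real deficit could then be missed on data that would have shown it under a better-aimed analysis.

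A smaller issue follows. Two of the ANOVA effects could be read as evidence of disease, and nothing says which one decides.

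**Working it through.** The protocol states no power or panel-wide error figure for the mouse work, so there is none to reproduce. The stated level is 0.05. Group size, number of tests, correlation and effect size below are assumptions.

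**Power: inputs.** n = 10 mice per group; three tests (one baseline, two post-immunisation); variance 1 at each test; equal correlation ρ = 0.5 within mouse; true group difference 0, 1, 1 SD; two-sided 5%. λ is the noncentrality parameter of the F test.

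1. *Group effect, baseline as a time level.* Mean difference = (0 + 1 + 1)/3 = 0.667. Variance of a mouse's mean = (1 + 2ρ)/3 = 0.667. λ = 0.667² / (0.667 × 2/10) = 3.33 on (1, 18) df. Power 0.41.
2. *Interaction.* The difference profile minus its mean is (−0.667, 0.333, 0.333), with sum of squares 0.667. λ = (n/2) × 0.667/(1 − ρ) = 5 × 0.667/0.5 = 6.67 on (2, 36) df. Power 0.59 (0.60 by simulation).
3. *Group effect on the two later tests only, no adjustment.* Variance of the mean = (1 + ρ)/2 = 0.75. λ = 1/(0.75 × 2/10) = 6.67 on (1, 18) df. Power 0.69.
4. *Mean of the two later tests, adjusted for baseline.* Residual variance = (1 + ρ)/2 − ρ² = 0.75 − 0.25 = 0.50. λ = 1/(0.50 × 2/10) = 10 on (1, 17) df, slightly reduced for chance baseline imbalance. Power 0.83. The simulated null rate of this contrast is 0.05 to 0.06.

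**Sensitivity to the correlation**, same formulas:

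| ρ | Group effect | Interaction | Baseline-adjusted |
|---|---|---|---|
| 0.2 | 0.54 | 0.40 | 0.78 |
| 0.5 | 0.41 | 0.59 | 0.83 |
| 0.7 | 0.35 | 0.82 | 0.93 |

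The adjusted contrast leads throughout. Which ANOVA effect comes second depends on ρ.

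**Does the baseline inflate false positives?** Simulation under no effect (20,000 runs, 10 per group, 3 to 6 tests, ρ = 0.5) gives a rate for group effect or interaction of 0.097 to 0.102 with the baseline in the time factor and 0.096 to 0.101 without it. The group effect alone stays at about 0.05 either way. So it does not.

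**Two effects, one paradigm.** Treated as independent, 1 − 0.95² = 0.0975. Simulation gives 0.097 to 0.102 under equal correlation, and 0.101 to 0.122 under first-order autoregressive correlation of 0.7 without a sphericity correction.

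**Across a panel, only if any single positive test counted.** With K independent paradigms, the rate is 1 − 0.95^K for one effect each and 1 − 0.95^(2K) for either of two effects:

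| K (assumed) | One effect | Either of two |
|---|---|---|
| 4 | 0.19 | 0.34 |
| 6 | 0.26 | 0.46 |
| 8 | 0.34 | 0.56 |

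These are upper values. Correlated paradigms give less, and single-time paradigms have no interaction to choose. One deciding effect per paradigm with Bonferroni across K returns about 0.049.

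**The case against.** Repeated-measures two-way ANOVA is a legitimate method for this design. The deciding effect, a primary paradigm and the multiplicity family are details that an analysis plan not shown here could settle. The second part of this stands, which is why the missing rule is a secondary matter here. The choice of model is different: section 8 makes it, so it can be questioned.

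A reader might infer that the behavioural claim carries a false-positive rate far above 5%. The documents do not support that. It needs a rule that any positive test suffices, and a number of paradigms; the protocol gives neither. Hypothesis 3 says "We postulate that the alterations in all these paradigms will be long-lasting", after a list that also contains inflammatory, antibody and synaptic changes. That wording reads as several lines of evidence together, and requiring concordant results would give less than 5%. A reader might also count the baseline as a cause of inflation; the simulation shows it is not. Nor does every paradigm pass through the two-way ANOVA, since single-time tests have their own methods.

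Multiplicity control is also not absent. If Bonferroni-corrected post-hoc group contrasts were the deciding tests, one paradigm would sit at 0.040 to 0.045. The text does not make them decisive and does not say whether the family spans paradigms, so this answers the error point only in part.

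Finally, the power figures assume that every mouse has both later tests. Mice euthanised at day 42 cannot, and the protocol does not name days 42 and 71 as behavioural test days. That limits the exact figures and shapes the fix.

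**Conclusion.** The point holds as a loss of power. If the pre-immunisation score is a level of the time factor, which is an inference from the schedule, the planned ANOVA gives about 0.41 (group effect) or 0.60 (interaction), where a baseline-adjusted contrast on the same mice gives 0.83. These values rest on 10 mice per group, one baseline and two later tests with complete data, correlation 0.5 and a sustained 1 SD effect. The ordering in favour of the adjusted contrast is the same at correlations of 0.2 and 0.7.

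Secondarily, if either the group effect or the interaction may be read as disease, the error per repeated-measures paradigm is about 10%. It would be higher over the panel if one positive test were enough. Both statements are conditional on rules that the protocol does not contain. The matter concerns objective 3 only and has no bearing on the human comparison.

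**What to change.** In section 8 (Animal studies), for paradigms with a pre-immunisation score, replace the two-way ANOVA as the deciding analysis with one contrast: peptide versus adjuvant-only over the post-immunisation behavioural tests, adjusted for each mouse's baseline score. Fit it in a mixed model, so that mice euthanised at day 42 contribute the tests they have. List in advance which post-immunisation tests enter the contrast. Make it the single deciding test per paradigm; time-course effects can still be reported descriptively. State that the Bonferroni correction already planned (or Holm) runs across paradigms, or name the paradigms that decide and label the others exploratory.

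The cost is a change of wording and of model on data already to be collected, with no extra mice. The downsides are a smaller p-value threshold for each paradigm, and some loss of sensitivity to a short-lived effect, because the contrast averages over the later tests. Hypothesis 3 expects lasting changes, so the second is acceptable.
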